6.2.4 Preparation

The CC Pharmacy will prepare ICG for infusion". The drug is supplied in a kit (NDC 17478-701-02) containing six 25 mg IC-GREEN vials and six 10mL Aqueous Solvent ampules. NDC 17478-701-25 IC-Green vial. 25 mg fill in 50 mL vial. NDC 17478-701.

7 STUDY INTERVENTION DISCONTINUATION AND PARTICIPANT DISCONTINUATION/WITHDRAWAL

7.1 DISCONTINUATION OF STUDY INTERVENTION

Off-Treatment Criteria:

- Completion of biopsy and biopsy observation period (typically no more than a 6-hour stay in the recovery area after the biopsy procedure)
- Participant requests to be withdrawn from the biopsy procedure.

- Allergic reaction (as described in section 8.5) and serious adverse event that is definitely related to the research.
- Unacceptable toxicity per PI
- Investigator discretion
- Loss of capacity to provide informed consent

7.2 PARTICIPANT DISCONTINUATION/WITHDRAWAL FROM THE STUDY

Off-Study Criteria:

- 1 ± 2 months of the completed biopsy (for all correlative pathological assessment of biopsy specimen availability)
- Participant requests to be withdrawn from study
- Death

8 STUDY ASSESSMENTS AND PROCEDURES

8.1 SCREENING PROCEDURES

The target study population is patients with focal hepatic lesions with imaging features suspicious for hepatocellular carcinoma or other metastatic liver disease. A radiologist will review patients' imaging for disease appropriate for biopsy. The decision to refer the patient to enroll in this study may occur between during tumor boards or other clinical care meeting where the primary care team, consults with a CC Interventional Radiologist/ AI or PI, Chief of CC/Interventional Radiology.

The research team will review and verify the following available information prior to patient registration on the protocol:

1. Clinical evaluation by referring team/ primary care team
2. Laboratory tests (blood work)
3. Radiology tests with report of focal lesions within the liver and confirmed or suspicious HCC other liver neoplasms or metastasis

8.2 REGISTRATION PROCEDURES

The Principal Investigator, along with key research personnel, will screen and enroll all eligible patients on the study. The screening and enrollment process will be documented in CRIS. All patients enrolled in the study will receive a unique patient identifier and will be entered in the study's screening and enrollment logs which are kept in our research database. The study research database will be maintained in an electronic folder in a larger central shared drive with a secure password and Clinical Center network back-up, in accordance with NIH CC policy.

8.3 TREATMENT ASSIGNMENT AND RANDOMIZATION/STRATIFICATION PROCEDURES COHORTS

Cohorts

Number	Name	Description
1	Patients	Patients scheduled for liver biopsy

Arms

Number	Name	Description
1	Interventional therapy	Liver biopsy with optical imaging and EM tracking guidance

8.4 EFFICACY ASSESSMENTS**8.4.1 Biospecimen Evaluations**

We will be using concordance with pathology as gold standard by measuring TBR (See Statistical section). ICG measurements to obtain the TBR will be done in vivo and ex vivo inside the IR suite. Specimens for pathology will be evaluated for quality and for diagnosis by NCI Laboratory of Pathology. No biospecimens will be collected and stored specifically for our research.

8.5 ADVERSE EVENTS AND SERIOUS ADVERSE EVENTS

To comply with the abbreviated IDE regulations 21 CFR 812.2(b), records concerning adverse device effects should include anticipated and unanticipated events and complaints.

Exceptions to adverse event data collection:

- Expected events related to the clinical biopsy procedure (for example, but incomplete list):
 - Pain or bruising at the biopsy site.
 - Increased redness, swelling or bloody or serosanguinous drainage at the biopsy site.
 - Events directly related to local anesthetic administration such as nausea, dizziness, numbness or tingling.
 - Self-resolved transient hypotension or bradycardia.
 - Diaphoresis
 - Headache
 - Pruritus
 - Skin discoloration at the intravenous site.

8.5.1 Definition of Adverse Event**8.5.1.1 Adverse Event**

Any untoward medical occurrence in a human subject, including any abnormal sign (for example, abnormal physical exam or laboratory finding), symptom, or disease, temporally associated with the subject's participation in research, whether or not considered related to the subject's participation in the research.

8.5.1.2 Adverse Device Effect

An adverse device effect (ADE) is an AE related to the use of our devices under study: the Karl Storz devices, Stryker® IRF Light Source and Safelight Cable, UroNav, or PercuNav.

8.5.1.3 Unanticipated Adverse Device Effect

Defined as any serious adverse effect on health or safety or any life-threatening problem or death caused by, or associated with, a device, if that effect, problem, or death was not previously identified in nature, severity, or degree of incidence in the investigational plan or other unanticipated serious problem associated with a device that relates to the rights, safety and welfare of subjects.

8.5.2 Definition of Serious Adverse Events (SAE)

8.5.2.1 Serious Adverse Event

An adverse event or suspected adverse reaction is considered serious if in the view of the investigator or the sponsor, it results in the following:

- death
- serious deterioration of the subject's health, leading to:
 - life-threatening illness or injury, or
 - permanent impairment of a body structure or function, or
 - in-patient or prolonged hospitalization, or
 - medical or surgical intervention to prevent life-threatening illness or injury or permanent impairment of a body structure or function

8.5.2.2 Serious Adverse Device Effect (SADE)

A serious adverse device effect (SADE) is an ADE that results in any of the consequences characteristic of an SAE. An unanticipated SADE (USADE) is a SADE which is not anticipated by the risk analysis, while an anticipated SADE (ASADE) is a SADE which is anticipated by the risk analysis.

8.5.3 Classification of an Adverse Event

For adverse events (AEs) not included in the protocol defined grading system, the following guidelines will be used to describe severity.

8.5.3.1 Severity of the Event

- **Mild** – Events require minimal or no treatment and do not interfere with the participant's daily activities.
- **Moderate** – Events result in a low level of inconvenience or concern with the therapeutic measures. Moderate events may cause some interference with functioning.
- **Severe** – Events interrupt a participant's usual daily activity and may require systemic drug therapy or other treatment. Severe events are usually potentially life-threatening or incapacitating. Of note, the term "severe" does not necessarily equate to "serious"

8.5.3.2 Relationship to Study Intervention

All adverse events (AEs) must have their relationship to study intervention assessed by the investigator who examines and evaluates the participant based on temporal relationship and his/her clinical judgment. The degree of certainty about causality will be graded using the categories below. In a clinical trial, the study product must always be suspect.

- **Definitely Related** – There is clear evidence to suggest a causal relationship, and other possible contributing factors can be ruled out. The clinical event, including an abnormal laboratory test result, occurs in a plausible time relationship to study intervention administration and cannot be explained by concurrent disease or other drugs or chemicals. The response to withdrawal of the study intervention (dechallenge) should be clinically plausible. The event must be pharmacologically or phenomenologically definitive, with use of a satisfactory rechallenge procedure if necessary.
- **Probably Related** – There is evidence to suggest a causal relationship, and the influence of other factors is unlikely. The clinical event, including an abnormal laboratory test result, occurs within a reasonable time after administration of the study intervention, is unlikely to be attributed to concurrent disease or other drugs or chemicals, and follows a clinically reasonable response on withdrawal (dechallenge). Rechallenge information is not required to fulfill this definition.
- **Potentially Related** – There is some evidence to suggest a causal relationship (e.g., the event occurred within a reasonable time after administration of the trial medication). However, other factors may have contributed to the event (e.g., the participant's clinical condition, other concomitant events). Although an AE may rate only as "possibly related" soon after discovery, it can be flagged as requiring more information and later be upgraded to "probably related" or "definitely related", as appropriate.
- **Unlikely to be related** – A clinical event, including an abnormal laboratory test result, whose temporal relationship to study intervention administration makes a causal relationship improbable (e.g., the event did not occur within a reasonable time after administration of the study intervention) and in which other drugs or chemicals or underlying disease provides plausible explanations (e.g., the participant's clinical condition, other concomitant treatments).
- **Not Related** – The AE is completely independent of study intervention administration, and/or evidence exists that the event is definitely related to another etiology. There must be an alternative, definitive etiology documented by the clinician.]

8.5.3.3 Expectedness

The Principal Investigator will be responsible for determining whether an adverse event (AE) is expected or unexpected. An AE will be considered unexpected if the nature, severity, or frequency of the event is not consistent with the risk information previously described for the study intervention.

8.5.4 Time Period and Frequency for Event Assessment and Follow-Up

The occurrence of an adverse event (AE) or serious adverse event (SAE) may come to the attention of study personnel during study visits and interviews of a study participant presenting for medical care, or upon review by a study monitor.

As this is a feasibility study, only grade 3 and above adverse events that are possibly, probably and definitely related to the research procedure (i.e., use of biopsy assisting devices and ICG administration) will be recorded, and reported if applicable. Given the decades' long use of the ICG as an approved agent, and the dose range used, which is often less than what is used clinically, we do not anticipate any toxicity.

All applicable AEs as described above, including local and systemic reactions not meeting the criteria for SAEs will be captured on the appropriate case report form (CRF). Information to be collected includes event description, time of onset, clinician's assessment of severity, relationship to study product (assessed only by those with the training and authority to make a diagnosis), and time of resolution/stabilization of the event. All recordable AEs occurring while on study must be documented appropriately. All reportable AEs will be followed to adequate resolution.

Any medical condition that is present at the time that the participant is screened will be considered as baseline and not reported as an AE. However, if the study participant's condition deteriorates at any time during the study, it will be recorded as an AE.

Changes in the severity of an AE will be documented to allow an assessment of the duration of the event at each level of severity to be performed. AEs characterized as intermittent require documentation of onset and duration of each episode.

8.5.5 Adverse Event Reporting

Adverse event monitoring will be performed from the time the consent is obtained until the patient is off treatment (4-6 hours post biopsy procedure). Adverse event reporting will be performed during this timeframe. Any reported Grade 3 and above adverse events that are possibly, probably, and definitely related to the research procedure, will be followed until resolution or stabilization.

8.5.6 Serious Adverse Event Reporting

The study investigator shall complete an Unanticipated Adverse Device Effect Form and submit to the study sponsor and to the reviewing Institutional Review Board (IRB) as soon as possible, but in no event later than 7 calendar days after the investigator first learns of the effect. The study sponsor is responsible for conducting an evaluation of an unanticipated adverse device effect and shall report the results of such evaluation to the Food and Drug Administration (FDA) and to all reviewing IRBs and participating investigators within 10 working days after the sponsor first receives notice of the effect. Thereafter, the sponsor shall submit such additional reports concerning the effect as FDA requests.

8.6 UNANTICIPATED PROBLEMS

8.6.1 Definition of Unanticipated Problems (UP)

Any incident, experience, or outcome that meets all of the following criteria:

- Unexpected in terms of nature, severity, or frequency given (a) the research procedures that are described in the protocol-related documents, such as the Institutional Review Board (IRB)-approved research protocol and informed consent document; and (b) the characteristics of the participant population being studied; and
- Related or possibly related to participation in the research ("possibly related" means there is a reasonable possibility that the incident, experience, or outcome may have been caused by the procedures involved in the research); and
- Suggests that the research places participants or others (which many include research staff, family members or other individuals not directly participating in the research) at a

greater risk of harm (including physical, psychological, economic, or social harm) than was previously known or expected.

8.6.2 Unanticipated Problem Reporting

The investigator will report unanticipated problems (UPs) to the NIH Institutional Review Board (IRB) as per Policy 801.

8.6.3 NIH Intramural IRB Reporting of IND Safety Reports

Only IND Safety Reports that meet the definition of an unanticipated problem will need to be reported to the NIH Intramural IRB.

9 STATISTICAL CONSIDERATIONS

Three medical procedures will be conducted to diagnose liver lesions as benign/malignant (negative/positive):

- (1) Histopathology, using well-established standard procedures.
- (2) ICG fluorescent signal at the in-vivo site of biopsy using a combination of OMI and EM tracking.
- (3) ICG fluorescent signal ex vivo of the specimen obtained using a combination of OMI and EM tracking.

For (2) and (3), malignancy determination will be based on TBR: $TBR \geq 2$ will produce a malignant diagnosis, and $TBR < 2$ will produce a benign diagnosis.

One main objective is to evaluate the agreement between (1) and (2), and between (1) and (3), with (1) considered as the gold standard. Since determinations are dichotomous, Cohen's kappa will be used to assess agreement.

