2.3.5 Results of pilot clinical trial for hepatic lesion sampling with optical guidance

Partners at MGH recently conducted the first-in-man trial of clinical liver biopsies using percutaneous OMI following injection of ICG ([Figure 7](#)). They recruited 6 patients for this pilot study [1]. The median size of the targeted lesions was 16 mm (range, 10–21 mm). Four of five biopsies (80%) yielded a positive pathologic diagnosis, and one biopsy specimen showed benign liver parenchyma.

[figure not shown]

Figure 7. Focal hepatic lesions on, A, MR image and, B, US image. C, 18F FDG PET scan shows avid lesions suspected of being malignancy. Intraprocedural optical molecular images confirmed the accuracy of the biopsy needle placement, by measuring increased fluorescence, E, in the target lesion relative to, D, normal liver. Optical images of the core biopsy specimen show visualized area of, F, focally increased ICG localization, G, in the core specimen. Final pathologic analysis of the core specimens revealed a granulomatous process.

[figure not shown]

Figure 8. Plot of normalized ICG

days following the procedures. We have shown that ICG imaging using these systems is a robust

Intraprocedural imaging of ICG fluorescence intensity at the tip of a standard introducer needle and within core biopsy specimens was feasible and added less than 5 minutes of procedure time in all patients. ICG was found to localize with TBRs greater than 2.0 (range, 2.4–13.4; median, 7.9) in all target lesions including primary HCC, metastatic CRC, and a non-neoplastic granulomatous process (Figure 8).

The difference between ICG fluorescence intensity between normal liver and focal hepatic lesions across the study cohort approached significance ($P = .06$). No trial-specific adverse events were observed up to 7

adjunct to conventional image guidance for patients undergoing biopsy of primary HCC, hepatic CRC metastasis, and non-neoplastic inflammatory processes, as well as thermal ablations.

[figure not shown]

Figure 9. NIH Clinical Center setup for an ultrasound/computed tomography –guided biopsy procedure with electromagnetic tracking guidance. FG: electromagnetic filed generator, NS: navigation.

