4 STUDY DESIGN

4.1 OVERALL DESIGN

This is a non-randomized, open-label prospective pilot study to evaluate the feasibility of the combination of optical molecular imaging (OMI) and EM tracking to guide liver biopsies and to detect and measure fluorescent ICG during intrahepatic biopsies. The primary endpoint is the concordance between the histopathology and measured ICG signal (typically TBR by handheld OMI for HCC). Concordance will be evaluated by confirming that all 4 of the following exist:

1. Diagnostic tissue specimen is obtained for conventional pathology analysis, defined by pathologist report of diagnostic liver lesion tissue
2. Imaging confirms that biopsy was taken from region desired
3. An ICG optical signal is obtained by ICG apparatus
4. EM tracking fusion image displays a location of biopsy.

Based on our preliminary data a TBR cut off value of 2.0 is typically considered positive for presence of malignant pathology. We expect that fluorescence intensity measurements will be able to accurately differentiate between benign and malignant lesions. This initial study will enroll 77 participants who have focal hepatic lesions suspicious for HCC or other metastatic liver disease, and for whom based on their primary research protocol, are directed to have a percutaneous diagnostic and or research biopsy.

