6.1.4.7 Handheld Ocular Molecular Imaging (OMI) device

This is the FDA cleared endoscopic device that is placed through the standard outer cannula introducer (outer part of the FDA cleared coaxial needle system). At no time does an experimental device touch the patient, in any way. The standard flexible and blunt-tip pediatric cystoscope-urethroscope “stylet/camera” is placed inside the introducer cannula to the predetermined length, in order to sample the tissue just immediately at the tip of the outer needle (see **Figure 6**). This tip of the pediatric cystoscope-urethroscope is like a non-sharp blunt felt-tip pen tip that cannot pierce the skin or tissue with normal forces of gentle manual manipulation, as is intended. It is a hand-held device used by an experienced interventional radiology physician who is certified and credentialed to practice (image guided therapy) interventional radiology. The camera and safelight cable are never inserted into the patient’s tissue beyond the ~ 1mm tip of the 17 Gauge outer cannula coaxial needle. The tissue (just beyond the pediatric cystoscope-urethroscope tip in the lesion) is sampled by the standard spring-loaded biopsy needle.

Liver biopsy is an invasive technique, with a well-described risk profile, and will be performed as clinically indicated and per the standards of the medical procedure. The 2 pauses to take signal sample with standard devices during the biopsy, is of non-significant risk (or minimal risk) in the opinion of the Principal Investigator the research team and others during the institutional scientific review process. The FDA-cleared pediatric cystoscope-urethroscope is not normally used via this needle cannula, tube, or lumen, but it is compatible.

The OMI is a handheld endoscopic instrument consisting of an FDA-cleared and clinically used pediatric cysto-urethroscope (Model 27033 AA; Karl Storz, Tuttlingen, Germany) illuminated by a safelight cable attached to an 808 nm laser excitation source (Stryker IRF L10 Light Source

and Safelight Cable) with an adjustable user feature in the Endoscopic Near-Infrared visualization (ENV) mode that can pass coaxially through the introducer of a standard 17-gauge core biopsy system (**Figure 6**).

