9.2 SAMPLE SIZE DETERMINATION

Based on the null kappa value $k_0=0.4$, a kappa value $k_1=0.7$ worth detecting, alpha (Type I error) equal to 0.05, 80% power, and a prevalence (true positive rate) of 80%, the resulting sample size from a one-sided test is 77.

Generally, $\kappa=0.4$ is considered as fair/moderate agreement, and $\kappa=0.7$ as substantial agreement.¹ With an 80% true positive rate, $\kappa=0.4$ corresponds to an 86% sensitivity and 55% specificity, and $\kappa=0.7$ corresponds to a 93% sensitivity and 80% specificity

With data on 77 cases, it is worthwhile determining the optimal cut-off point for TBR to confirm whether $TBR=2$ is optimal. This can be done based on Youden's index in receiver operating characteristic (ROC) analysis.

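### Concordance has two unreconciled definitions, so a missed-target core is a match under one and a failure under the other, and the kappa test has no rule for it

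*Combined protocol and SAP*

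**What the plan says.** Section 9 introduces the analysis with "Three medical procedures will be conducted to diagnose liver lesions as benign/malignant (negative/positive"). It allows two pathology results and two TBR results (at least 2, or below 2), and adds: "Since determinations are dichotomous, Cohen's kappa will be used to assess agreement". Section 9.1 defines concordance as the proportion of imaging and pathology results that match, and assumes 80% malignant and 20% benign. Section 9.2 sizes the trial: "Based on the null kappa value $k_0=0.4$, a kappa value $k_1=0.7$ worth detecting", with "alpha (Type I error) equal to 0.05, 80% power, and a prevalence (true positive rate) of 80" percent, one-sided, giving 77. Section 9.4.1 treats everyone who completes the biopsy as evaluable for objective response.

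Sections 4.1 and 9.4.3 define concordance differently, as four conditions that must all hold. The first is "Diagnostic tissue specimen is obtained for conventional pathology analysis, defined by pathologist report of diagnostic liver lesion tissue". The others are imaging confirmation of the sampled region, an ICG signal, and an EM display of the biopsy location.

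The target of inference also varies. Section 4.1 says: "We expect that fluorescence intensity measurements will be able to accurately differentiate between benign and malignant lesions". The secondary objectives in Sections 1.1 and 3 concern the signal at the biopsy site against malignancy as pathology defines it there.

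**The concern.** The in vivo reading and the core share one needle position. Section 6.1.4.7 says: "The tissue (just beyond the pediatric cystoscope-urethroscope tip in the lesion) is sampled by the standard spring-loaded biopsy needle". If the tip is in normal liver, the reading can be liver over liver (TBR near 1) and the core normal parenchyma. Both are then negative for a reason unrelated to whether the lesion is malignant.

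Section 9 has no class for such a core. If it is filed as benign, it enters the smallest part of the table (about 15 of 77 patients, 20%), where kappa is most sensitive. If the list in 4.1 and 9.4.3 governs, the same record is a failure. Section 9.4.2 has analysis running alongside enrolment, so the choice could be made after data are seen. What is at stake is whether rejecting kappa ≤ 0.4 shows that TBR separates benign from malignant lesions, or partly reflects how often the needle missed.

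**Working it through.** **Reproducing the plan.** Let τ be the large-sample standard deviation of kappa with both marginals at 80%. Then n = [(1.645·τ0 + 0.842·τ1)/(0.7 − 0.4)]², with τ0 = 1.128 and τ1 = 0.904. This gives (2.616/0.3)² = 76.03, rounded up to 77. The sensitivity and specificity pairs in Section 9.2 also reproduce: 86%/55% gives kappa 0.394 and 93%/80% gives 0.709. The sample size is not in question.

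**Null device without misses.** At 80% malignant and 86%/55%, the cells are TP 0.688, FN 0.112, FP 0.090, TN 0.110, and concordance is 0.798.

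**Adding 10% misses, all reading TBR below 2 (match rule, Section 9.1).**
- The cells become 0.619, 0.101, 0.081 and 0.099 + 0.100 = 0.199.
- Concordance = 0.9 × 0.798 + 0.1 = 0.818.
- Chance agreement = 0.720 × 0.700 + 0.280 × 0.300 = 0.588.
- Kappa = (0.818 − 0.588)/(1 − 0.588) = 0.559.

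**Same data, item 1 failure counted as non-concordant.** Concordance = 0.9 × 0.798 = 0.718. Read literally, the four conditions never look at the match. They could then all be met in up to 90% of patients (1 − 0.10), including every lesion core where TBR and pathology disagree.

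**Effect on the test.** The miss rate is an assumption, because the documents state none. Rejection rates come from exact enumeration of all 2×2 tables at n = 77. The rule is to reject if (kappa − 0.4)/SE > 1.645, with SE estimated from the data. The share of misses reading TBR ≥ 2 (with a normal core) is varied:

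| Misses reading TBR ≥ 2 | 5% misses: kappa, rejection | 10% misses: kappa, rejection |
|---|---|---|
| none | 0.489, 21% | 0.559, 45% |
| a quarter | 0.446, 12% | 0.484, 21% |
| half | 0.402, 6% | 0.406, 7% |
| all | 0.308, 1% | 0.234, 0.2% |

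With no misses, rejection is 5.4%. The plan does not name the test form. With the null standard error instead, the first-row figures are 13% and 30%, against 3.4% with no misses.

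**Plausibility of 5-10%.** Section 4.2 cites negative predictive values of 72% and 63%, so 28% to 37% of benign biopsies were false negatives. With 20% benign, that is 0.20 × 0.28 = 5.6% to 0.20 × 0.37 = 7.4% of patients. Not all of that shortfall need be targeting error.

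**Lesion-tissue cores only.** The null device is then rejected in 3.3% to 6.3% of trials across miss rates of 0-30%, depending on test form. Power with the Wald test at 93%/80% is 85% with 77 pairs, 82% with 69 (10% misses) and 80% with 62 (20% misses), if 80% of the remaining cores are malignant. At kappa 0.7 with equal marginals, it is 75-79% with 69 pairs and 70-77% with 62, by test form.

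If the 10% removed all come out of the plan's 20% benign share, 0.80/0.90 = 89% of the 69 are malignant. Concordance is then 0.916, chance agreement 0.771, kappa 0.144/0.229 = 0.63, and power about 48%.

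**The case against.** Four points against the concern carry weight.

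- A reader might infer that Section 9 scores every missed target as correct agreement. It does not say so. Section 9.4.3 would reject a core without lesion tissue, and Section 9.3.2 defines TBR with a numerator taken inside the lesion, so a miss has no proper TBR. What stands is that the plan never says whether those conditions gate the kappa table, count as failures in it, or form a separate feasibility measure.
- Under the site-level objective, normal liver read as negative is genuine agreement. This stands in full. The match misleads only when reported as a lesion diagnosis, which is how Sections 4.1 and 9 word it.
- A near miss may still fluoresce. The phantom in Section 2.3.1 showed signal through 10 mm, although Section 2.2 gives 0.5 cm as the working limit. In the pilot (Section 2.3.5) "one biopsy specimen showed benign liver parenchyma", yet TBR exceeded 2.0 in all target lesions. That does not support assuming that every miss reads low, and it ties no core to a needle miss.
- Restricting the test to lesion cores can cost much power, as the 48% figure shows. A lesion-only kappa should not be adopted as the sole tested result without restating power.

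**Conclusion.** The concern holds as a conflict of definitions with a material consequence. The same patients can give 82% or 72% concordance at 10% misses, and nothing decides which rule feeds the kappa.

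It is tempting to conclude that the bias always favours the device. The documents do not support that. Inflation to 21-45% needs every miss to read TBR below 2. It largely disappears when half read 2 or more and reverses when all do. What holds in general is that a kappa containing no-lesion cores depends on targeting as well as on discrimination.

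The figures rest on the plan's null performance (86%/55%, 80% malignant), n = 77, a one-sided 5% Wald test and an assumed miss rate of 5-10%. The calculation of 77 is sound for the quantity it was built on.

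**What to change.** - In Sections 4.1 and 9.4.3, make the lesion-tissue condition a requirement for entering the lesion-agreement analysis. Keep a single definition of concordance, the TBR/pathology match in Section 9.1.
- In Section 9, classify pathology as malignant lesion, benign lesion or no lesion tissue, using the pathology report already required.
- Report kappa for all cores (site level) and for lesion-tissue cores only. List the no-lesion cores separately, with how many read TBR below 2 and how many at least 2.
- State before analysis which kappa is tested against 0.4. Claim benign-versus-malignant lesion discrimination only if the lesion-only kappa supports it.
- Attach the stated 80% power to the all-cores analysis and restate it for the lesion-only one.

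No new data are needed. The cost is precision in the lesion-only result: power of 82% with 69 pairs or 80% with 62 if the malignant share stays at 80%, but about 48% with 69 if the removed cores are all from the benign share. Keeping 77 lesion pairs would take 77/0.9, or 86 enrolled, at 10% misses, and 77/0.8, or 97, at 20%. Those counts preserve the number of pairs, but not the power if the benign share shrinks.
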